### *Planned analyses*

Population: Analyses will be performed on all included patients with data available regarding the remission and flare status questions.

For remission, all included patients with data available regarding remission will be assessed. The primary analysis is on baseline data. The data from the second visit will be seen as confirmatory and will be analysed as longitudinal data accounting for multiple visits.

For flare, only patients with both visits completed will be used. Change in outcomes between the 2 visits will be assessed.

Similarly to what has been done in axial spondyloarthritis (and differently to what has been done in rheumatoid arthritis), it is decided that flare will be defined as a change in status between the 2 time points, i.e., a flare is an absolute or relative change between 2 values: the observed value of the outcome at the time of the flare, minus the referral value (previous status before the flare). (Gossec2016, Bykerk2016)

The patient's initial status (referral value of the outcomes at the first visit) may vary from no symptoms to moderate/high disease activity but we will analyse separately patients with very high initial values, since it is considered that definitions of flares are only relevant for patients initially not in very high disease activity.

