#### Inclusion criteria

- Age > 18 years
- Definite PsA according to the CIASSification of Psoriatic ARthritis (CASPAR) criteria and diagnosis confirmed by a rheumatologist. (Taylor2006)
- Willingness to participate and signed informed consent.
- There are no inclusion criteria based on disease activity or treatment. Given the international study with countries with varied levels of health and of access to care and treatments, the study should include patients with a wide range of disease severity and activity at baseline.
- Patients with more than 2 years of disease duration will be included in the study for more homogeneity.

Patient will be included consecutively. A registry will be kept locally to note the age and gender of patients who have been proposed the study but refused to participate.

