### Treatment changes

Physicians will collect patient treatments for PsA and will answer if the treatment is changed or not and in which way (i.e., intensification, yes/no) at each visit.

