#### *Flare*

Only flares at the time of assessment are targeted (and not recall of previous flares).

To assess flares from the patient perspective, the preliminary GRAPPA flare instrument will be evaluated: 1.A recent change in joint pain.2.A recent change in location of symptoms (i.e., sudden increase in pain or swelling in hands/feet).3.A recent change in the number of tender and/or sore joints. 4. A recent change in the

number of aching joints. 5. The presence or degree of pressure-sensitive joints. 6. A recent change/increase in the number of swollen joints. 7. A recent change/increase in night pain. 8. A recent change/increase in the number or combination of symptoms (**Table 1**). (Moverly2016a)

Patient will also answer a specific targeted question on their assessment of flare yes/no (see above).

The Minimum Clinically Important Difference (MCID) question gives information on change in disease status. The question is: "How would you describe your overall status since your last visit: much better, better, the same, worse, much worse?" Here, worse or much worse will be used to define a flare. (Curtis2015)

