### Planned analyses:

Cutoff values for each outcome and for each change in outcome will be calculated using ROC curves and 75th percentile analyses (**Table 2 and 3**). For ROC curves, different cutoffs will be calculated, both using Youden's statistic (maximizing both sensitivity and specificity) but also using a fixed specificity number (80%) since specificity is more important than sensitivity in this case (to avoid overdiagnosing

flares). The 75th percentile technique is a classical technique which finds the value above which, 75% of patients reporting an outcome or a change in outcome, are placed. Rasch analysis will be used as appropriate. (Tubach2005, Machado2016) These techniques are widely used to determine cutoff values for continuous scores and are recommended by COSMIN (Mokkink2016/ website.cosmin)

Sensitivity analyses will explore cutoff values found according to patient demographic characteristics and country.

We will compare attainment of remission/low disease activity or flare according to the different definitions, using kappa analyses and logistic regression analyses will explore characteristics of patients who are in 'discordance' or not for flare/remission with the physician-defined definition, and physicians who are in 'discordance' with patients as well.

Missing data: All data will be analysed. To minimize missing data, the order of questions will also be studied to motivate respondents to finish the entire questionnaire.

**Table 2.** Planned analyses: defining cutoff values according to different definitions of remission/low disease activity (LDA)

Gold standards are below	MDA	Modified versions of MDA	Physician Gobal Assessment	DAPSA/c-DAPSA	PASDAS	Modified AMDF	PsAID	HAQ	Pain	Fatigue	PGA	SF12
MDA												
modified versions MDA												
Physician remission/LDA single questions												
Physician Global Assessment<4/10												
Composite score DAPSA												
Composite score PASDAS												
PASS												
Patient remission/LDA single questions												

**Table 3.** Planned analyses: defining cutoff values for change of outcomes according to different definitions of flare

Gold standards are below	MDA	Physician global ass.	DAPSA/c-DAPSA	PASDAS	Modified AMDF	GRAPPA flare questionnaire	PsAID	HAQ	Pain	Fatigue	PGA	SF12
Treatment intensification												
Physician flare single question												
Composite score DAPSA change in category												

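### The flare change analysis admits patients already positive at visit 1 on a status-type anchor, so their change is not measured from a pre-flare value

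*Combined protocol and SAP*

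**What the plan says.** The population paragraph of Planned analyses gives one condition for the flare set: "For flare, only patients with both visits completed will be used. Change in outcomes between the 2 visits will be assessed". It continues: "it is decided that flare will be defined as a change in status between the 2 time points". The explanation that follows is in terms of the outcome score: "the observed value of the outcome at the time of the flare, minus the referral value (previous status before the flare". Visit 1 supplies that reference value.

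The only rule that looks at baseline is "we will analyse separately patients with very high initial values". It goes by score level, gives no threshold and does not use flare status.

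Patients can be in flare at visit 1. Inclusion criteria: "There are no inclusion criteria based on disease activity or treatment". The flare anchors describe the present: "Only flares at the time of assessment are targeted (and not recall of previous flares". Table 1 lists the physician and patient flare questions at both visits, and under Treatment changes physicians "will answer if the treatment is changed or not and in which way (i.e., intensification, yes/no) at each visit". Treatment intensification is the physicians' gold standard for flare.

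On the second visit, the Brief synopsis, the Long Summary, Patients' recruitment and Data collection all have each patient seen or assessed twice, with no exception. The Sample size section, explaining why fewer patients will contribute to flares, says that those whose treatment was intensified are not assessed again. The Budget section expects 450 baseline and 400 second visits.

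**The concern.** A change score measured from a pre-flare state needs a patient who was not in flare at visit 1. The population rule does not require this. Two groups cause trouble for a status-type anchor:

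- **Persisting flares** (positive at both visits). If counted as cases, they add changes near zero and pull the cutoff down.
- **Resolving flares** (positive, then negative). They sit among the controls with large falls in score. This lowers the cutoff that gives 80% specificity, which the plan wants because "since specificity is more important than sensitivity in this case".

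MCID worsening and DAPSA or PASDAS category change are change measures already and are spared. The GRAPPA items ask mostly about recent change, so that instrument may be partly affected. For treatment intensification, the reader also cannot tell whether patients intensified at visit 1 are in the flare set at all.

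**Working it through.** **1. The plan's own counts.** n = (1.96 × SD / precision)². With SD 2.30 this gives the stated 82 at a precision of 0.5; the printed 0.05 gives 8,129 (a separate matter). 82 / 0.20 = 410, as stated. With the budgeted 400 second visits, 400 × 0.20 = 80 flares.

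**2. Model for the class rule.** The documents give no persistence, flare effect or visit-to-visit noise, so all of these are assumed.
- Stable PsAID level N(3, SD 1.8), plus 2.0 when in flare, plus independent noise of SD 0.9 at each visit.
- 20% in flare at each visit. The plan gives 20% in flare overall; applying it to both visits is an assumption.
- Persistence = share of visit 1 flares still in flare at visit 2: 10% / 25% / 40%. P(new flare) = (0.20 − 0.20 × persistence) / 0.80 = 0.225 / 0.188 / 0.150.
- Visit 1 scores of 7 or more set aside, standing in for the plan's undefined very high values.

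The plan's 75th-percentile cutoff is the value exceeded by 75% of flare cases, that is, the 25th centile of their change. Hand check for new flares before any set-aside: SD of change = 0.9 × √2 = 1.27, so the cutoff is 2.0 − 0.674 × 1.27 = 1.14. The simulation with the set-aside gives 1.17.

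**3. Results by case rule.** The reference takes new flares as cases and patients negative at both visits as controls.

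| Cutoff (PsAID points) | Reference | All completers, by visit 2 status | New flares as cases, all visit 2 negatives as controls |
|---|---|---|---|
| 75th percentile | 1.17 | 0.96 / 0.62 / 0.25 | unchanged (1.16–1.18) |
| 80% specificity | 1.09 | 0.89 / 0.93 / 0.96 | 0.89 / 0.93 / 0.96 |
| Youden | 1.02 | 0.83 / 0.84 / 0.85 | 0.86 / 0.90 / 0.94 |

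Among patients flare-free at both visits, the nominal 80% cutoff has specificity 0.75–0.77.

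**4. Against sampling error** (half the 2.5–97.5% range over simulated studies of 400).
- 75th percentile: half-width 0.40–0.51. The falls are 1.17 − 0.96 = 0.21, 1.17 − 0.62 = 0.55 and 1.17 − 0.25 = 0.92. The last two exceed it; the first does not.
- 80% specificity: half-width 0.21–0.23; shifts 0.13–0.20.
- Youden: half-width about 0.6–0.8; shifts at most about 0.2.

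**5. Sensitivity to the assumptions.**
- Very high threshold: at 25% persistence the 75th-percentile fall is about 0.55 with a threshold of 7, 0.46 with 6 and 0.37–0.39 with 5. The last is within sampling error.
- Share in flare at visit 1: the 80%-specificity shift is 0.05–0.10 at 10% and 0.20–0.33 at 30%, so at 30% it can exceed sampling error.
- A second model (within-state correlation 0.7, no set-aside) gives a 75th-percentile cutoff of 0.87 for new flares, against 0.37 / −0.13 / −0.53 by visit 2 status at 20% / 40% / 60% persistence. The direction is the same.

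**6. Second visits.** 450 − 400 = 50 patients (11%) without a second visit, for whatever reason. If 10% / 20% / 30% of 450 were intensified at visit 1 (assumed) and not seen again, at most 405 / 360 / 315 remain. At 20% in flare that is 81 / 72 / 63 flares. The half-width 1.96 × 2.30 / √n is then 0.50 / 0.53 / 0.57.

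**The case against.** The strongest reply is that the intent is clear. A patient in flare at both visits has no change of status and no pre-flare value, so the definition already rules out persisting flares as cases. On that reading the 75th percentile is untouched and the base-case ROC shifts are within sampling error. Much of this stands: classing everyone by visit 2 status is the less natural reading. But the plan explains the change as a difference in scores, its population rule asks only for two visits, and neither reading settles where resolving flares belong.

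The separate analysis of very high starting scores helps, and more so with a lower threshold. It still does not act on flare status.

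A reader might infer that the Sample size section flatly contradicts the statements that everyone is seen twice. The documents do not support that. Planned analyses also uses *assessed* to mean analysed, and the sentence concerns the size of the analysed sample. Patients intensified at visit 1 could be seen twice and left out of the flare analysis. The wording conflicts with the other sections only if it means not seen.

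It is also fair that the two single flare questions are sensitivity anchors and that the plan calls the flare analysis exploratory.

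**Conclusion.** The point holds as a mismatch between the population rule and the plan's own definition of flare change, for status-type anchors. If all completers are classed by visit 2 status, the 75th-percentile cutoff comes out too small: by about 0.2 to 0.9 PsAID points over 10–40% persistence in the base case. That is beyond sampling error at 25% and 40% with a very high threshold of 7, but not at 25% with a threshold of 5. If only new flares are cases, that cutoff is unaffected and the base-case ROC shifts lie within sampling error. Every model input is assumed, so these figures show direction and possible size; they are not a forecast.

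A reader might infer that all the planned flare cutoffs are biased. They are not: MCID worsening and the category changes are spared, and GRAPPA is at most partly affected. The second-visit wording is an ambiguity to reconcile, not a proven contradiction. It matters because it decides who enters the analysis of the physicians' gold standard.

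**What to change.** In the population paragraph of Planned analyses:

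- For each status-type anchor, restrict the main flare analysis to patients negative on that anchor at visit 1. Cases are positive at visit 2 and controls negative at visit 2.
- Keep all completers, including persisting and resolving flares, as a sensitivity analysis.
- State whether the rule applies to the GRAPPA instrument. Leave MCID worsening and the category changes as they are.
- Give the score threshold for very high initial values, since the size of the effect depends on it.

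Reconcile the Sample size section with the Brief synopsis, Long Summary, Patients' recruitment, Data collection and Budget: do patients intensified at visit 1 have second-visit data, and are they in the flare set? Restate the expected number of flares accordingly.

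The cost is wording only, because the anchors are already recorded at both visits. There are fewer cases: in the illustrative model about 47–70 new flares per 400, against 74–77 flares in all after the set-aside. A reader might expect this to cost precision, but in that model the 75th-percentile half-width is 0.40–0.49 for new flares against 0.42–0.51 for all cases, because mixing in persisting flares widens the spread of change. Improving patients leave the main control group, so the reported specificity applies to patients not in flare at visit 1.

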### Planned analyses:

Cutoff values for each outcome and for each change in outcome will be calculated using ROC curves and 75th percentile analyses (**Table 2 and 3**). For ROC curves, different cutoffs will be calculated, both using Youden's statistic (maximizing both sensitivity and specificity) but also using a fixed specificity number (80%) since specificity is more important than sensitivity in this case (to avoid overdiagnosing

flares). The 75th percentile technique is a classical technique which finds the value above which, 75% of patients reporting an outcome or a change in outcome, are placed. Rasch analysis will be used as appropriate. (Tubach2005, Machado2016) These techniques are widely used to determine cutoff values for continuous scores and are recommended by COSMIN (Mokkink2016/ website.cosmin)

Sensitivity analyses will explore cutoff values found according to patient demographic characteristics and country.

We will compare attainment of remission/low disease activity or flare according to the different definitions, using kappa analyses and logistic regression analyses will explore characteristics of patients who are in 'discordance' or not for flare/remission with the physician-defined definition, and physicians who are in 'discordance' with patients as well.

Missing data: All data will be analysed. To minimize missing data, the order of questions will also be studied to motivate respondents to finish the entire questionnaire.

**Table 2.** Planned analyses: defining cutoff values according to different definitions of remission/low disease activity (LDA)

Gold standards are below	MDA	Modified versions of MDA	Physician Gobal Assessment	DAPSA/c-DAPSA	PASDAS	Modified AMDF	PsAID	HAQ	Pain	Fatigue	PGA	SF12
MDA												
modified versions MDA												
Physician remission/LDA single questions												
Physician Global Assessment<4/10												
Composite score DAPSA												
Composite score PASDAS												
PASS												
Patient remission/LDA single questions												

**Table 3.** Planned analyses: defining cutoff values for change of outcomes according to different definitions of flare

Gold standards are below	MDA	Physician global ass.	DAPSA/c-DAPSA	PASDAS	Modified AMDF	GRAPPA flare questionnaire	PsAID	HAQ	Pain	Fatigue	PGA	SF12
Treatment intensification												
Physician flare single question												
Composite score DAPSA change in category												
Composite score PASDAS change in category												
GRAPPA flare questionnaire												
Patient flare single question												
Worsening MCID												

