**There are several definitions of remission and acceptable residual disease activity levels in PsA.** (Kavanaugh2006, Acosta2014) The Group for Assessment of Psoriasis and Psoriatic Arthritis (GRAPPA) suggested that remission in PsA should be characterized by “a complete absence of disease activity, with no signs or symptoms of active disease”. (Kavanaugh2006) In parallel, the European League Against Rheumatism (EULAR) defined remission in PsA as “the absence of clinical and laboratory evidence of significant inflammatory disease activity.” (Gossec2016a) Contrary to the situation in rheumatoid arthritis where a specific definition of remission has been proposed by a European League Against Rheumatism (EULAR)/American College of Rheumatology (ACR) consensus (Aletaha2010a, Bykerk2012), in PsA a specific and quantifiable definition of remission is lacking. However some approaches have been proposed recently based on physician consensus exercises and using composite disease activity scores. Remission and low disease activity definitions have been defined using the Disease Activity index for Psoriatic Arthritis (DAPSA) (Aletaha2016b) The DAPSA is composed of five untransformed, unweighted variables, including two patient-centered items (patient global assessment and pain on an 11-point numeric rating scale), one physician centered item (swollen joint count using 66 joints, 66-SJC), one item dependent on patient and physician (tender joint count using 68 joints, 68-TJC), and a laboratory variable (C Reactive Protein (CRP) in mg/dL). (Aletaha2016b) The DAPSA-based remission status (i.e., a score <4 points) is associated with no or minimal residual ultrasound signals in the joints. (Schoels2016) A clinical DAPSA score (c-DAPSA) is also available and is calculated using the same variables as DAPSA, without CRP. Other measures with validated definitions of remission include the Composite Psoriatic Disease Activity Index (CPDAI), the GRAPPA-developed PsA Disease Activity Score (PASDAS) and Arythmetic Mean of Desirability Functions (AMDF). (Mumtazz2011, Helliwell2014)

An alternative treatment target is Minimal Disease Activity (MDA). Minimal disease activity (MDA), agreed at the Outcome Measures in Rheumatology Clinical

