### *Unidimensional PROs*

Patient Global Assessment (PGA) (on a 0–10 scale) asks the patient to give an overall assessment of how the arthritis is doing, thereby integrating a number of dimensions related to disease activity or to other aspects. The wording of questions and anchors are usually as follows: for the PGA, 'Considering all of the ways your arthritis affects you, mark "X" on the scale for how well you are doing' ('very well' to 'very poor').

Patient global for skin and for joints will also be evaluated on a numeric scale from 0 to 10 since part of the AMDF. (Helliwell2013) This will also give some indication on patient-perceived skin involvement.

Pain will be evaluated on a numeric scale from 0 to 10.

Fatigue will be analysed also (it is included in the PsAID).

The HAQ-Disability index is a disability questionnaire which includes 8 domains scored on a 0-3 scale (0 = without any difficulty, 1 = with some difficulty, 2 = with much difficulty, 3 = unable to do). (Pincus2007)

The validated single questions to define Minimal Clinically Important Difference (MCID) and PASS will be assessed as explained above.

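### The percentile cutoff rule contradicts itself: it is named the 75th percentile but defined as the 25th, and neither reading suits both remission levels and flare changes

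*Combined protocol and SAP*

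**What the plan says.** Under Statistical analyses, the second Planned analyses subsection states: "Cutoff values for each outcome and for each change in outcome will be calculated using ROC curves and 75th percentile analyses". It then explains the percentile method as a classical technique "which finds the value above which, 75% of patients reporting an outcome or a change in outcome, are placed". The Brief synopsis and the Long Summary repeat the 75th-percentile name without defining it.

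The same rule serves two tables. Table 2 is for "defining cutoff values according to different definitions of remission/low disease activity (LDA)", that is, baseline levels. Table 3 is for "defining cutoff values for change of outcomes according to different definitions of flare". The first Planned analyses subsection fixes the sign of a change: "the observed value of the outcome at the time of the flare, minus the referral value".

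No list of score directions is given, but several directions can be read from the text:

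- **DAPSA:** Background gives remission as a score below 4, so low is good.
- **HAQ:** Unidimensional PROs gives "0 = without any difficulty, 1 = with some difficulty, 2 = with much difficulty, 3 = unable to do", so low is good.
- **Patient global assessment:** the anchors run from very well to very poor, so low is good.
- **Pain:** Background uses an upper limit for pain within MDA, so low is good.
- **SF-12:** Composite PROs calls these health and well-being scores but does not state the direction.

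**The concern.** The name and the definition identify opposite quartiles. Correcting only one of them does not repair the plan, because the tail that is needed depends on two things the rule ignores: whether the cutoff is for a level or for a worsening, and whether a high score is good or bad.

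Defining cutoffs is the study's objective, and the percentile method is one of only two named routes to them, for every outcome and every change. The protocol intends the cutoffs for clinical use and for interpreting later trials. A cutoff from the wrong tail would be presented as the value that most patients in remission, or most patients in flare, attain, when only a minority attain it.

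**Working it through.** **Step 1: label against description.** If P(X > c) = 0.75, then P(X ≤ c) = 1 − 0.75 = 0.25, so c is the 25th percentile. This needs no assumption about the data.

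**Step 2: which percentile puts 75% of the reference group on the intended side.** The reference group is the patients who meet the remission or flare definition. The change is the later value minus the earlier one.

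| Use | Score direction | Percentile needed | Label (75th) | Description (25th) |
|---|---|---|---|---|
| Remission level | low is good | 75th | works | wrong tail |
| Flare change | low is good (worsening is positive) | 25th | wrong tail | works |
| Remission level | high is good | 25th | wrong tail | works |
| Flare change | high is good (worsening is negative) | 75th | works | wrong tail |

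The first two rows use only directions found in the document (DAPSA, HAQ, pain, patient global). The last two apply to SF-12 if high is good, which is an assumption. MDA is a yes/no state, so a percentile does not apply to that column. The direction of the modified AMDF is not given.

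**Step 3: distance between the readings (normal score assumed).**

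- Gap = 2 × 0.6745 × SD = 1.349 SD.
- Standard error of a quartile at n = 82 (from Sample size) = √(0.25 × 0.75 / 82) / 0.3178 = 0.150 SD, where 0.3178 is the normal density at the quartile. The 95% half-width is 1.96 × 0.150 = 0.295 SD.
- Ratio = 1.349 / 0.295 = 4.6.
- In PsAID points, an assumed SD within remission of 1.2, 1.5 or 1.8 gives a gap of 1.62, 2.02 or 2.43. The plan's SD of 2.30 would give 3.10, but it is not specific to patients in remission.

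A skewed score reduces the ratio. With gamma shapes of (mean, SD) = (1.0, 1.0), (1.5, 1.2), (2.0, 1.5) and (2.5, 2.3), all assumed, the quartiles are 0.29 and 1.39, 0.62 and 2.05, 0.90 and 2.71, and 0.84 and 3.46. The gaps are 1.10, 1.43, 1.81 and 2.62 points, or 1.10 to 1.21 SD. Putting the gamma density at the upper quartile into the same formula, the gap is 2.9 to 3.3 times that quartile's half-width.

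**Step 4: share of patients meeting the cutoff.** On a continuous scale the wrong tail captures 25% and the right one 75%. Ties change this on whole-number scales. All means and SDs below are assumed.

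Remission on a 0–10 scale, normal and rounded, share at or below c = Φ((c + 0.5 − mean)/SD):

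| Mean, SD | 25th percentile | Share meeting it | 75th percentile | Share meeting it |
|---|---|---|---|---|
| 1, 1.2 | 0 | 34% | 2 | 89% |
| 1.5, 1.3 | 1 | 50% | 2 | 78% |
| 2, 1.6 | 1 | 38% | 3 | 83% |
| 2.5, 1.8 | 1 | 29% | 4 | 87% |
| 3, 1.8 | 2 | 39% | 4 | 80% |

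Flare change in whole points, positive is worse, share at or above c = 1 − Φ((c − 0.5 − mean)/SD):

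| Mean, SD | 75th percentile | Share reaching it | 25th percentile | Share reaching it |
|---|---|---|---|---|
| 1, 1.5 | 2 | 37% | 0 | 84% |
| 1.5, 1.5 | 3 | 25% | 0 | 91% |
| 2, 2 | 3 | 40% | 1 | 77% |
| 2.5, 2 | 4 | 31% | 1 | 84% |
| 3, 2 | 4 | 40% | 2 | 77% |

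The second flare row is a knife-edge: P(change ≤ 2) = Φ(1/1.5) = 0.7475, only just short of 0.75. Without it the ranges are 31–40% and 77–84%.

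**The case against.** The strongest reply is that this is a slip of wording in a well-known technique. An experienced analyst would take the 75th percentile for remission levels, which is the primary analysis and which the label serves on every score the document shows to be low-is-good. The description happens to serve flare on those same scores, and the plan itself calls the flare analysis exploratory. Two ROC cutoffs (Youden and fixed 80% specificity) stand beside each percentile cutoff as comparators. Harm arises only if one statement is applied mechanically throughout, and the text does not show that it will be.

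Much of this is fair. The plan is ambiguous, and no wrong analysis has yet been run. The sizes also carry limits: the ratio of 4.6 needs a normal score and is a multiple of the 95% half-width, not of the standard error; the flat 25% does not hold on coarse scales such as pain and patient global; and the flare extremes come from one knife-edge case.

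The reply does not remove the problem, because it relies on the analyst using the label for one table and the description for the other, and no passage says so. Reading "above" as better or worse has no support in the text, which speaks of a value. The stated wish to avoid overdiagnosing flares is the reason given for the fixed-specificity ROC cutoff and does not settle the percentile rule.

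**Conclusion.** The concern holds, and the rule should be corrected before the analysis is run. The contradiction between name and definition follows from the wording alone. That each reading fails in one of the two tables follows from directions the document itself gives. Only the further point, that each reading also fails within the other table, depends on SF-12 being scored so that high is good.

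The consequence is large: the wrong quartile turns a cutoff meant to capture about three quarters of the target patients into one that captures about a quarter, or up to half where ties are heavy. The displacement exceeds the sampling error of the estimate under both the normal and the skewed shapes tried. The exact shares and the PsAID-point gaps rest on assumed distributions. The ROC cutoffs, the data collected and the sample size are untouched.

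**What to change.** Replace the defining sentence with two direction-specific ones:

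- **Remission:** the cutoff is the score at or better than which 75% of patients meeting the remission definition lie. This is the 75th percentile where high is worse and the 25th where high is better.
- **Flare:** the cutoff is the amount of worsening reached or exceeded by 75% of patients meeting the flare definition. This is the 25th percentile of the change, with every score coded so that a positive change is a worsening.

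Add a one-column list of the direction of each score in Tables 2 and 3, including SF-12 and the modified AMDF, and mark the yes/no MDA column as not applicable to this method. With each percentile cutoff, report the share of reference patients who actually meet it, since ties on 0–10 scales move it away from 75%.

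The cost is two sentences and a short list, fixed before the tables are run. Data collection, sample size and the ROC analyses do not change.
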